Packaging and Labeling	Study drug will be provided in glass vials. Each glass vial will be labeled as required per country requirement.	

DMC = Data Monitoring Committee; IV = intravenous; Q3W = every 3 weeks

NOTE: Refer to the Pharmacy Instructions for further details.

NL-201 will be administered until unacceptable toxicity, disease progression, withdrawal of consent, patient or physician decision, or study termination. Patients with progressive disease who have experienced clinical benefit from NL-201 will have the option to continue on therapy past progression.

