Planned NL-201 Dose Levels^b			
1A	1B	0.1	10
2A	2B	0.3	30
3A	3B	1.0	100
4A	4B	3.0	300
5A	5B	6.0	600
6A	6B	12.0	1200
Potential NL-201 Intermediate Dose Levels^b			
2A-1	2B-1	0.6	60
3A-1	3B-1	1.5	150
3A-2	3B-2	2.0	200
4A-1	4B-1	4.0	400
4A-2	4B-2	5.0	500
5A-1	5B-1	7.5	750
5A-2	5B-2	9.0	900
5A-3	5B-3	10.0	1000

D = day; DMC = Data Monitoring Committee; IV = intravenous.

a Applicable to patients that weigh ≥ 100 kg (dose is capped as to not allow > 100 times the current dose level to be administered to a patient at 1 time).

b At the recommendation of the DMC or based on Sponsor's determination, additional dose levels may be tested and/or cohorts may be expanded.

The maximum tolerated dose (MTD) is defined as the highest dose for which the probability of a patient experiencing a DLT with NL-201 during Cycle 1 is $\leq 33\%$. At the discretion of the DMC, and in keeping with the pre-specified mTPI design matrix, additional dose levels may be tested to determine the MTD.

Based on review of DLTs, the DMC may initiate step-dosing to improve the tolerability of NL-201, wherein 1 or more step-doses below the target dose would be provided prior to reaching the target dose (see Section 6.2.1.4). If step-dosing is used, the DLT window would extend from the first dose to 21 days after receiving the target dose (ie, would include the initial reduced-dose cycles in addition to the first target-dose cycle). Once a patient receives the intended target dose for their cohort, subsequent doses for that patient will continue at that dose level unless a delay in dosing of > 6 weeks causes washout of the drug, in which case the step-dosing regimen would be repeated if the patient is to resume dosing.

Supported by the mTPI design, the DMC will determine the RP2D and treatment schedule (IV Schedule A, IV Schedule B) for Part 2 by considering the PK, PDn, tolerability, antitumor activity, and the occurrence of any cumulative toxicities over multiple cycles of NL-201.

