6.2.2 Dosage Adjustments, Delays, Rules for Withholding or Restarting, Permanent Discontinuation

6.2.2.1 NL-201 Dosage Adjustments, Delays, Rules for Withholding or Restarting, Permanent Discontinuation

Patients that experience a DLT may be dose-reduced or withdrawn from the study after discussion with the medical monitor. The reason for dose change of NL-201 is to be recorded on each patient's case report form (CRF). Dose escalation patients and expansion patients may also experience delays, reductions and other dose adjustments. Dose may be delayed up to 21 days; any delay beyond 21 days must be approved by the medical monitor. If Cycle 2 is skipped, then PK, antitumor activity, cytokines, and PDn samples should still be collected at the next cycle according to the Cycle 2 schedule and documented as unscheduled visits.

Refer to [Table 11](#) for guidance on toxicity management and dose modifications.

For Parts 3 and 4, refer to [Section 6.2.2.2](#) for guidance on withholding NL-201 when given in combination with pembrolizumab.

Table 11 Dose Delay^a and Modification Guidance for IV Administration

Potential Toxicity	Dose Modification if Grade ≤ 2	Dose Modification if Grade ≥ 3
Chills		Hold dose until Grade ≤ 2
Fever		Hold dose until Grade ≤ 2
Pruritis		No change
Nausea/vomiting/anorexia		Hold dose until Grade ≤ 2
Diarrhea		Hold dose until Grade ≤ 2
Gastritis/stomach upset		Hold dose until Grade ≤ 2
Malaise		Hold dose until Grade ≤ 2 if other Grade ≥ 3 toxicities occur simultaneously
Anemia		Hold dose until Grade ≤ 2 or return to baseline
Leukocytosis		Hold dose until leukocyte count $< 100,000/\text{mm}^3$
Thrombocytopenia		Hold dose until Grade ≤ 2
Edema/weight gain		No change
Hypotension		Hold dose until Grade ≤ 2 , resume 1 dose level lower. Stop treatment if vasopressor support is required.
Capillary leak syndrome		Hold dose until Grade ≤ 2
Cytokine release syndrome	Hold dose until recovery to Grade 1. Pre-medication should be adjusted per Section 6.1.3 . NL-201 dosing may be resumed at the same dose.	Grade 3: Hold dose until recovery to Grade 1. Pre-medication should be adjusted per Section 6.1.3 . NL-201 dosing may be resumed at the same dose. If Grade 3 recurs and cannot be managed with supportive measures including the use of steroids with short biological half-life (eg, prednisone), dose must be reduced by one dose level for subsequent doses after discussion with Medical Monitor. Grade 4: Stop treatment

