Infusion-related reaction or hypersensitivity reaction	Stop infusion immediately. Consider treatment with diphenhydramine and/or acetaminophen. Infusion may be resumed after Grade 2 reaction has resolved with slower infusion rate. Pre-medication should be adjusted per Section 6.1.3 .	Grade 3: Consider treatment with diphenhydramine and/or acetaminophen and/or systemic steroids per institutional standard practice. If infusion reaction occurs and it can be adequately managed with supportive measures, the patient may be continued on the study with pre-medication adjusted per Section 6.1.3 for subsequent doses. Otherwise, stop treatment. If Grade 3 recurs and cannot be managed with supportive measures including steroids, dose must be reduced by 1 dose level for subsequent doses. Grade 4: Stop treatment

ANC = absolute neutrophil count; IV = intravenous.

a Dose may be delayed up to 21 days; any delay longer than 21 days must be approved by medical monitor

b Refer to [Section 10.5](#) if drug-induced liver injury is suspected.

6.2.2.2 Pembrolizumab Dosage Adjustments, Delays, Rules for Withholding or Restarting, Permanent Discontinuation

6.2.2.2.1 Dose Modification and Toxicity Management for Immune-Related AEs Associated with Pembrolizumab

AEs associated with pembrolizumab combination exposure, including coadministration with additional compounds may represent an immune-related response. These irAEs may occur shortly after the first dose or several months after the last dose of pembrolizumab combination treatment and may affect more than one body system simultaneously. Therefore, early recognition and initiation of treatment is critical to reduce complications. Based on existing clinical study data, most irAEs were reversible and could be managed with interruptions of pembrolizumab combination treatment, administration of corticosteroids and/or other supportive care. For suspected irAEs, ensure adequate evaluation to confirm etiology or exclude other causes. Additional procedures or tests such as bronchoscopy, endoscopy, skin biopsy may be included as part of the evaluation. Dose modification and toxicity management guidelines for irAEs associated with pembrolizumab are provided in [Table 12](#).

Attribution of Toxicity:

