8 STUDY ASSESSMENTS AND PROCEDURES

- Only patients who meet all inclusion and exclusion criteria specified in [Section 5](#) will be enrolled in this study.
- Study procedures and their timing are summarized in the Schedule of Events ([Section 1.3](#)).
- Immediate safety concerns should be discussed with the Sponsor immediately upon occurrence or awareness to determine if the patient should continue or discontinue study drug.
- Adherence to the study design requirements, including those specified in the Schedule of Events, is essential and required for study conduct.
- All screening evaluations must be completed and reviewed to confirm that potential patients meet all eligibility criteria. The Investigator will maintain a screening log to record details of all patients screened and to confirm eligibility or record reasons for screening failure, as applicable. **ECOG and laboratory evaluations required for Cycle 1 Day 1 (within 48 hours prior to dosing) must conform to the following criteria prior to first dose of study drug on Cycle 1 Day 1:**
 1. Patients with ECOG performance status of 0 or 1
 2. Platelets $\geq 100,000/\text{mm}^3$
 3. ANC $> 1500/\text{mm}^3$
 4. Hemoglobin: Parts 1 and 2: ≥ 8.0 g/dL; Parts 3 and 4: ≥ 9.0 g/dL (NOTE: Criteria must be met without packed red blood cell transfusion within the prior 2 weeks. Participants can be on stable dose of erythropoietin [\geq approximately 3 months]).
 5. Lymphocyte count $\geq 500/\text{mm}^3$
 6. Eosinophils $< 1000/\text{mm}^3$

7. Renal function: eGFR \geq 50 mL/min/1.73 m² as determined by 2009 CKD-EPI equation,²⁹ or creatinine WNL
 8. AST and ALT: Parts 1 and 2: \leq 3x ULN, or \leq 5x ULN if known liver malignancy or metastasis; Parts 3 and 4: \leq 2.5x ULN, or \leq 5x ULN if known liver malignancy or metastasis
 9. TBL WNL, or \leq 3x ULN if known Gilbert's syndrome
 10. Coagulation: INR OR PT \leq 1.5 x ULN
 11. Highly sensitive pregnancy test (serum or urine) confirming no pregnancy
- Procedures conducted as part of the patient's routine clinical management (eg, blood count) and obtained before signing of the ICF may be utilized for screening or baseline purposes, provided the procedures met the protocol-specified criteria and were performed within the time frame defined in the Schedule of Events.

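### Table 11 stops NL-201 for a Grade 3 infusion reaction that cannot be managed, yet prescribes only a one-level reduction when such a reaction recurs despite steroids

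*Combined protocol and SAP*

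**What the plan says.** Section 6.2.2.1 refers sites to Table 11 for toxicity management and dose modification of NL-201. Table 5 also names Table 11 as the place for managing infusion-related reactions.

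For a Grade 3 infusion-related or hypersensitivity reaction, after suggesting drug treatment, the cell gives three rules in this order:

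- The first is for a manageable reaction: "If infusion reaction occurs and it can be adequately managed with supportive measures, the patient may be continued on the study". Pre-medication is then adjusted for later doses.
- The second and third follow directly, for any other case and for a recurrence: "Otherwise, stop treatment. If Grade 3 recurs and cannot be managed with supportive measures including steroids, dose must be reduced by 1 dose level". The reduction applies to whatever doses come after.

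At Grade 4 the same cell ends treatment.

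Other text bears on the same patient:

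- Section 6.2.2.1, on DLTs: "Patients that experience a DLT may be dose-reduced or withdrawn from the study after discussion with the medical monitor".
- Section 6.1.1, on how long NL-201 is given: "NL-201 will be administered until unacceptable toxicity, disease progression, withdrawal of consent, patient or physician decision, or study termination".
- Section 8, on urgent safety matters and the choice between continuing and stopping: "Immediate safety concerns should be discussed with the Sponsor immediately upon occurrence or awareness to determine if the patient should continue".
- Section 7.1 lists adverse events among the reasons for removal from study drug.

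**The concern.** The second and third rules both apply to a Grade 3 reaction that has come back and cannot be managed. One ends NL-201. The other sets the level at which later doses are to be given. A site reading the cell cannot tell which rule governs, and two sites could each follow it and act in opposite ways.

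What is at stake is the safety of individual patients. The row covers hypersensitivity as well as infusion reactions. Its most specific instruction for a reaction that recurred and did not yield to steroids speaks of further dosing, whereas a first reaction that could not be managed ends treatment.

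**Working it through.** No arithmetic applies and the plan states no figure to reproduce. The check is to set the sentences side by side and follow each patient through them.

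**Step 1: what stopping treatment means here.** The same row tells sites to stop the infusion immediately for a reaction of Grade 2 or below, and to stop treatment for Grade 4. The two phrases are kept apart, so stopping treatment in the Grade 3 cell means ending NL-201, not pausing an infusion.

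**Step 2: the action for each patient under the two possible readings.**

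| Grade 3 reaction | Literal reading (the stop rule covers every occurrence) | Sequential reading (the stop rule covers the first occurrence only) |
|---|---|---|
| First, manageable | Continue with adjusted pre-medication | Continue with adjusted pre-medication |
| First, not manageable | Stop | Stop |
| Recurrent, not manageable even with steroids | Stop, and also reduce one level for later doses | Reduce one level for later doses |

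On the literal reading, the last row holds two incompatible instructions. On the sequential reading it holds one, but that one is milder than the instruction for a first unmanageable reaction.

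**Step 3: whether other text settles it.**

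- The DLT sentence in Section 6.2.2.1 allows either reduction or withdrawal and does not say which Table 11 sentence governs. DLT definitions in Section 6.2.1.3 exist only for Parts 1 and 3 and are tied to the DLT window, so expansion patients and later recurrences are not clearly covered.
- Sections 6.1.1 and 8 give general discretion to stop. They do not interpret the cell.
- Section 7.1 points back to the dose-modification guidance in Section 6.2.2 for toxicities that require permanent discontinuation, which returns the reader to the same cell.
- Table 13 allows no further dosing after a Grade 3 reaction, but it covers pembrolizumab only.

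**Step 4: the nearest comparator.** The cytokine release syndrome row of Table 11 has almost the same recurrence rule: a one-level reduction if Grade 3 recurs and cannot be managed, steroids included. It differs in two ways. No stop rule for an unmanageable Grade 3 event comes before it, and the reduction follows discussion with the Medical Monitor. That row is internally consistent. The infusion-reaction row adds the stop rule and omits the Medical Monitor step.

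**The case against.** The strongest reply is that the cell should be read in order. The stop rule closes the test applied when a reaction first occurs, and only a patient who was allowed to continue can have a recurrence. The specific recurrence sentence then governs, and each patient receives one instruction. This is a fair reading and it removes the strict contradiction. It does not explain why the repeat event, after steroids have also failed, is handled less strictly than the first.

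A second reply is that the cytokine release syndrome row shows the sponsor may have meant reduction for some recurrences. That stands as a possibility. The similar wording fits either a deliberate policy or text carried over from one row to the other, and the documents do not say which. It is a reason for the sponsor to state its intention.

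A third reply is that the protocol never orders another dose. This is right, and it limits the point. A reader might infer from the mandatory wording that investigators are obliged to re-dose such a patient. The documents do not support that. The sentence fixes the level of any later dose and presupposes that there will be one, but physician decision, unacceptable toxicity, adverse events and discussion with the sponsor all remain routes to stopping. Table 11 is also presented as guidance. These routes soften the rule without correcting it.

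**Conclusion.** The point holds as a defect in one cell of Table 11. Depending on the reading, the cell gives either two incompatible instructions or an inverted order of severity for a recurrent Grade 3 reaction that cannot be managed. Nothing else in the protocol says which is meant.

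The conclusion assumes that stopping treatment means ending NL-201, which the row's own vocabulary supports, and that the subsequent doses mentioned are further NL-201 doses. The number of patients affected cannot be estimated, because the documents give no frequency for such reactions.

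A reader might also infer that dose-finding is compromised. The documents do not support that: the cell governs what happens after the event, and in Part 1 a recurrent Grade 3 infusion reaction despite pre-medication within the DLT window is a DLT whichever action follows. No effect on DLT counts, the RP2D or any analysis is claimed.

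The matter deserves correction because it concerns patient safety and the remedy is small. The existing discretion to stop keeps it from being more serious.

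**What to change.** Reword the Grade 3 text of the infusion-related or hypersensitivity cell along these lines, keeping the opening advice on drug treatment:

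> If a Grade 3 reaction, whether first or recurrent, is adequately controlled by supportive measures including steroids, NL-201 may be continued with pre-medication adjusted under Section 6.1.3. After a recurrent reaction that was controlled, any dose reduction is decided with the Medical Monitor. If a reaction is not adequately controlled, first or recurrent, NL-201 is stopped.

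This removes the mandatory one-level reduction for a recurrence that cannot be managed.

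The sponsor should then look at the cytokine release syndrome row. Table 5 lists many of the same symptoms for both conditions, including fever, chills or rigors, headache, rash, arthralgia, myalgia and hypotension. After the change, a recurrent unmanageable Grade 3 event would mean stopping under one label and reducing under the other. The sponsor should confirm that this difference is intended, or align the rows.

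The cost is one reworded cell at the next amendment and a letter to sites. No new data, visits or procedures are needed. The downside is likely to be a few more discontinuations among patients whose recurrent Grade 3 reaction could not be managed.

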6.2.2.2.2 Dose Modification and Toxicity Management of Infusion-Reactions Related to Pembrolizumab

Pembrolizumab may cause severe or life-threatening infusion-reactions including severe hypersensitivity or anaphylaxis. Signs and symptoms usually develop during or shortly after drug infusion and generally resolve completely within 24 hours of completion of infusion. Dose modification and toxicity management guidelines on pembrolizumab associated infusion reaction are provided in [Table 13](#).

Table 13 Pembrolizumab Infusion Reaction Dose Modification and Treatment Guidelines

CTCAE Grade	Treatment	Pre-medication at Subsequent Dosing
Grade 1 Mild reaction; infusion interruption not indicated; intervention not indicated	Increase monitoring of vital signs as medically indicated until the participant is deemed medically stable in the opinion of the investigator.	None
Grade 2 Requires therapy or infusion interruption but responds promptly to symptomatic treatment (eg, antihistamines, NSAIDs, narcotics, IV fluids); prophylactic medications indicated for ≤ 24 hrs.	
 • Stop Infusion. • Additional appropriate medical therapy may include but is not limited to: 
 ○ IV fluids ○ Antihistamines ○ NSAIDs ○ Acetaminophen ○ Narcotics • Increase monitoring of vital signs as medically indicated until the participant is deemed medically stable in the opinion of the investigator. • If symptoms resolve within 1 hour of stopping drug infusion, the infusion may be restarted at 50% of the original infusion rate (eg, from 100 mL/hr. to 50 mL/hr.). Otherwise dosing will be held until symptoms resolve and the participant should be pre-medicated for the next scheduled dose. • Participants who develop Grade 2 toxicity despite adequate pre-medication should be permanently discontinued from further study drug treatment 	Participant may be pre-medicated 1.5h (± 30 minutes) prior to infusion of study intervention with: Diphenhydramine 50 mg po (or equivalent dose of antihistamine). Acetaminophen 500-1000 mg po (or equivalent dose of analgesic).

CTCAE Grade	Treatment	Pre-medication at Subsequent Dosing
Grades 3 or 4	
 Stop Infusion. Additional appropriate medical therapy may include but is not limited to: 
 Epinephrine** IV fluids Antihistamines NSAIDs Acetaminophen Narcotics Oxygen Pressors Corticosteroids 	No subsequent dosing
Grade 3: Prolonged (ie, not rapidly responsive to symptomatic medication and/or brief interruption of infusion); recurrence of symptoms following initial improvement; hospitalization indicated for other clinical sequelae (eg, renal impairment, pulmonary infiltrates)		
Grade 4: Life-threatening; pressor or ventilator support indicated	
 Increase monitoring of vital signs as medically indicated until the participant is deemed medically stable in the opinion of the investigator. Hospitalization may be indicated. **In cases of anaphylaxis, epinephrine should be used immediately. Participant is permanently discontinued from further study drug treatment.	

IV = intravenous; CTCAE = Common Terminology Criteria for Adverse Events; NSAID = non-steroidal anti-inflammatory drug

Appropriate resuscitation equipment should be available at the bedside and a physician readily available during the period of drug administration. For further information, please refer to the CTCAE V5.0 at <http://ctep.cancer.gov>.

6.2.2.2.3 Other Allowed Dose Interruption for Pembrolizumab

Pembrolizumab may be interrupted for situations other than treatment-related AEs such as medical or surgical events and/or unforeseen circumstances not related to study intervention. However, study intervention is to be restarted within 3 weeks or 21 days of the originally scheduled dose and within 42 days of the previously administered dose, unless otherwise discussed with the Sponsor. The reason for interruption is to be documented in the patient's study record.

6.3 Measures to Minimize Bias: Randomization and Blinding

6.3.1 Randomization

This is an open-label, dose escalation/dose expansion study; patients will not be randomized.

6.3.2 Blinding

This is an open-label study.

6.4 Study Drug Compliance

When patients are dosed at the site, they will receive study drug directly from the Investigator or designee, under medical supervision. The date and time of each dose administered in the clinic will be recorded in the source documents and recorded in the CRF. The dose of study drug and study patient identification will be confirmed at the time of dosing by a member of the study site staff other than the person administering the study drug.

6.5 Concomitant Therapy

Necessary supportive care, including antibiotics, blood products, IV fluids, anti-diarrheals, anti-emetics will be allowed per local standard of care. All treatments that the investigator considers necessary for a participant's welfare may be administered at the discretion of the investigator in keeping with the community standards of medical care.

Any medication or vaccine (including over-the-counter or prescription medicines, and/or herbal supplements) that the patient is receiving at the time of enrollment or receives during the study must be recorded along with:

- Reason for use
- Dates of administration including start and end dates (if known)
- Concomitant therapies of interest only and if available during the course of the study: dosage information including dose and frequency

The Medical Monitor should be contacted if there are any questions regarding concomitant or prior therapy.

All concomitant medications received within 28 days prior to the first dose of study treatment and up to 30 days after the last dose of study treatment will be recorded. All concomitant medications administered during SAEs or ECIs are to be recorded. SAEs and events of clinical interest (ECIs) are defined in [Section 8.4](#).

Participants should receive appropriate supportive care measures as deemed necessary by the treating investigator. Suggested supportive care measures for the management of AEs with potential immunologic etiology are outlined along with the dose modification guidelines in [Section 6.2.2.2.1](#).

Note: If after the evaluation of the event, it is determined not to be related to pembrolizumab, the investigator does not need to follow the treatment guidance. Refer to [Table 12](#) in [Section 6.2.2.2.1](#) for guidelines regarding dose modification and supportive care.

It may be necessary to perform conditional procedures such as bronchoscopy, endoscopy, or skin photography as part of evaluation of the event.

